All parts of this investigation utilise a standard infusion protocol of a study drug. This study drug will be isoprenaline or placebo delivered in a double blinded fashion or will be open label isoprenaline dependent on which experiment it is being administered for. In all cases the infusion protocol will be identical as will the associated outcomes recorded. Although different experiments within the protocol call for different, statistically driven endpoints, the endpoints for every administration of a study drug infusion protocol are the same.

Outcome after which infusion would be stopped

- Occurrence of atrial fibrillation lasting greater than 30 seconds during study drug infusion protocol
- Occurrence of an arrhythmia other than atrial fibrillation, sinus tachycardia or junctional rhythm lasting greater than 30 seconds during study drug infusion protocol
- Discontinuation of the study drug infusion
 - o Severe tremulousness or anxiety
 - Complaints of severe chest tightness
 - Decrease in systolic blood pressure to consistently < 70mmHg
 - Electrocardiographic changes suggestive of myocardial ischaemia

Pre-specified outcomes to be recorded but which would not trigger cessation of infusion

- Occurrence of atrial fibrillation lasting less than 30 seconds during study drug infusion protocol
- Occurrence of an arrhythmia other than atrial fibrillation, sinus tachycardia or junctional rhythm lasting less than 30 seconds during study drug infusion protocol
- Time from start of infusion protocol to occurrence of atrial fibrillation
- Rate of infusion at time of occurrence of atrial fibrillation
- Maximum tolerated rate of study drug infusion prior to its cessation for any reason

Safety Endpoints associated with each infusion administration

- Death within 24 hours of start of study drug infusion protocol
- Stroke within 24 hours of start of study drug infusion protocol
- Myocardial Infarction within 24 hours of start of study drug infusion protocol

Observational Data

Collected from Additional Monitoring Group

Participants from some groups recruited will be offered the chance to have some additional follow up monitoring after their ablation procedure. This data will be purely descriptive and unpowered. It will be analysed looking at the following endpoints.

Observational Endpoints

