The investigators are authorised to provide alternative treatment to that specified in the protocol at any stage if he/she feels it is in the participant's best interest. The reasons for deviation from protocol should be recorded.

Reasons for Discontinuation of Subject's Participation in Study

A subject can voluntarily discontinue their involvement in the study at any stage without the need to give reason and without prejudicing further treatment. In addition, subjects will be removed from the study if they cease to meet the inclusion criteria after enrolment (eg participant in SVT block has electrophysiology study that demonstrates atrial tachycardia rather than ANRT or AVNRT) or if they develop one of the exclusion criteria (eg require treatment with amiodarone in the time between the 2 infusions required for Protocol Part A). Subjects will also be excluded from continuation in the study if they develop anaphylaxis, chest pain or ECG features of myocardial ischaemia during the infusion protocol.

Where subjects withdraw or are excluded from the study after enrolment but prior to their completion of the study schedule, a further subject will be recruited to their subject group to take their place. Any data collected before withdrawal may be included in the study results.

End of Study Actions

Having withdrawn from the study, been excluded from continued participation or having completed their final visit or ambulatory ECG recording, participants will have completed their involvement in the study. There are no specific interventions required at completion of the study schedule. All participants will be informed that they may still contact the study team should they have questions or concerns regarding their health or their involvement in the study.

Safety Assessment

Adverse Events

Definitions

- Adverse Event (AE): any untoward medical occurrence in a patient or clinical study subject.
- Serious Adverse Event (SAE): any untoward and unexpected medical occurrence or affect that:
 - Results in death
 - Is life-threatening refers to an event in which the subject was at risk of death at the time of the event; it does not refer to an event which hypothetically might have caused death if it were more severe
 - Requires hospitalisation, or prolongation of existing inpatients' hospitalisation
 - Results in persistent or significant disability or incapacity
 - o Is a congenital anomaly or birth defect

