Medical judgement should be exercised in deciding whether an AE is serious in other situations. Important AEs that are not immediately life-threatening or do not result in death or hospitalisation but may jeopardise the subject or may require intervention to prevent one of the other outcomes listed in the definition above, should also be considered serious.

The MHRA Drug Analysis Print safety information on isoprenaline documents only 169 adverse drug reactions over 47 years of widespread clinical use in the UK. We would therefore consider all such events rare phenomena. The following list of adverse reactions is that described in the FDA approved product literature for Isuprel.

Source	Common	Uncommon	Rare
FDA Approved product literature for Isoprenaline	Nervousness Headache Dizziness Nausea Tachycardia Palpitations Hypertension Hypotension Tachyarrhythmias Dyspnoea Flushing of the skin Sweating Mild Tremors Pallor	Visual Blurring Weakness	Stokes Adams attacks Transient Heart block Pulmonary Oedema Ventricular Arrhythmias Angina

A number of the above reactions represent predictable, normal effects of isoprenaline or any similar sympathomimetic including endogenous adrenaline. They do not pose a risk to the health of the participant experiencing them and such experiences are described and quoted as being likely to occur in the Participant Information Sheets. As such we do not believe it to be useful to perform full adverse event reporting procedures for each occurrence. These events will be recorded on the case report form in all instances but will only be reported as an adverse event if it is felt that they represent a SAE or Suspected Unexpected Serious Adverse Reactions (SUSAR). The reactions which will be dealt with in this way are.

- Nervousness
- Tachycardia
- Palpitations
- Hypertension
- Hypotension
- Tachyarrhythmias
- Flushing of the skin
- Sweating
- Mild tremors
- Pallor

If any serious uncommon or rare adverse events occur the study will be suspended until the event is fully assessed by the Chief Investigator, Sponsor, Medicines and Healthcare Regulatory Agency (MHRA) and Research Ethics Committee (REC) as per the reporting procedure below.

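### The adverse-event exemption covers hypotension of any severity, although the protocol itself stops the infusion when systolic pressure stays below 70 mmHg

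*Protocol*

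**What the plan says.** The Adverse Events section of the protocol reproduces the reactions in the US product literature and picks out ten that it regards as predictable effects of the drug. Of these it says: "They do not pose a risk to the health of the participant experiencing them". It therefore sees no use in running the full reporting procedure each time. The ten reactions "will only be reported as an adverse event if it is felt that they represent a SAE" or a SUSAR. Recording is kept: "These events will be recorded on the case report form in all instances". Hypotension and nervousness stand on the list as bare terms. Tremor is listed only in its mild form.

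Infusion Endpoints, repeated under Infusion Protocol, gives four intolerance reasons for discontinuing the infusion. One is "Decrease in systolic blood pressure to consistently < 70mmHg" and another is "Severe tremulousness or anxiety". The other two are severe chest tightness and ischaemic ECG changes.

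The Adverse Events section also asks that an event be treated as serious, as a matter of medical judgement, where it "may jeopardise the subject or may require intervention to prevent one of the other outcomes listed in the definition above".

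**The concern.** The exemption rests on a statement about harm, and the stopping rule contradicts that statement for one of the exempt terms. A fall in pressure that obliges the team to stop the drug is not a harmless expected effect, yet it is exempt on the same terms as flushing or pallor. Unless someone feels it is serious, it need not be handled as an adverse event.

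What is at stake is oversight while the study runs. An adverse event brings review of the documentation, an entry in the medical notes, and an assessment of intensity, causality, expectedness and seriousness. Under Reporting procedure, an accumulation of minor events related to the study drug also makes a discussion with the sponsor and ethics committee mandatory. The protocol does not say whether exempt events count towards that accumulation.

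**Working it through.** No calculation applies and there is no figure in the plan to reproduce. The check compares the exempt list with the stopping reasons and then follows what happens to an event on each route.

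**Exempt terms.** The product-literature table has 14 common reactions. Ten are exempt: nervousness, tachycardia, palpitations, hypertension, hypotension, tachyarrhythmias, flushing, sweating, mild tremors and pallor. The remaining 14 − 10 = 4 (headache, dizziness, nausea, dyspnoea) are not. One of the ten, tremor, has a severity limit. That qualifier already stands in the table, so it may have been carried over rather than chosen.

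**Stopping reasons against exempt terms.**

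| Intolerance reason for stopping | Exempt term that covers it |
|---|---|
| Systolic pressure consistently below 70 mmHg | Hypotension: clear overlap |
| Severe tremulousness or anxiety | Tremulousness: none, since only mild tremor is exempt. Anxiety: not listed; covered only if read as nervousness |
| Severe chest tightness | None |
| ECG changes suggesting ischaemia | None |

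So one of the four reasons clearly falls under an exempt term, and one component of a second arguably does.

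**What happens to an infusion stopped for low pressure.**

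1. The stop reason, time to stopping, maximum rate and minute-by-minute blood pressure are recorded at every infusion (Infusion Protocol), and the reaction goes on the case report form. Nothing is lost from the data.
2. If it is felt to be an SAE or SUSAR, it is reported as such.
3. If it is not, the exemption applies and the full procedure is not required. A case of nausea or headache, not being exempt, would go through it.
4. Whether the event counts towards the multiple-minor-events trigger is left open.

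**Whether another provision closes the gap.** Reporting procedure opens by asking that all adverse events be reported. That general statement conflicts with the specific exemption and does not say which prevails. The intensity assessment is asked for, but intensity is not used to limit the exemption. The safety endpoints attached to each infusion are death, stroke and myocardial infarction within 24 hours, so they do not pick up hypotension.

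**The case against.** The strongest reply is that little is lost. For a non-serious event, Reporting procedure asks mainly for documentation review, recording, assessment and analysis at the end of the study; the 24-hour notice to the sponsor is for SAEs only. Exempt events are already recorded, with the pressure readings and the reason for stopping. This largely stands, and it is why the point is small. It does not remove the assessment step or the doubt about the trigger. One can argue that the trigger refers to adverse events in general, so that recorded but unreported ones count. That is a fair reading, but the text does not settle it.

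The second reply is the important-event clause. Sustained systolic pressure below 70 mmHg is a plain candidate for it, and judgement is how seriousness is normally decided. This also stands in part: it is a real backstop, but it works case by case, beside a sentence telling the same team that the reaction poses no risk. A reader might go further and infer that the SAE route is shut, because the definition speaks of "any untoward and unexpected medical occurrence or affect" and hypotension is listed as common. The documents do not support that. The important-event clause does not repeat the requirement, anticipated ablation complications are themselves called serious adverse events, and expectedness and seriousness are assessed as separate items.

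Two other inferences are tempting. One is that severe anxiety is exempt as well, making two stopping reasons out of four. Anxiety is not on the list, and equating it with nervousness is reasonable but is the reader's step. The other is that the exemption lets a participant go on to a second infusion after the first was stopped for low pressure. Continuation is governed by Reasons for Discontinuation of Subject's Participation in Study, under which participants are "excluded from continuation in the study if they develop anaphylaxis, chest pain or ECG features of myocardial ischaemia during the infusion protocol". Hypotension is absent there, but changing the reporting rule would not alter that list. In Part B both infusions fall within one procedure, so an adverse-event report would rarely intervene. Investigators may in any case depart from the protocol in the participant's interest.

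**Conclusion.** The point holds in a narrow form. The exemption treats hypotension of every severity as harmless, and the protocol's own stopping rule shows that it is not when systolic pressure stays below 70 mmHg. The consequence is a small loss of safety oversight: such an event may be recorded without the full adverse-event procedure, and its place in the multiple-minor-events trigger is unclear.

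No estimate, power or error rate changes. The protocol gives no rate of infusion-stopping hypotension, so the number of affected events cannot be stated; planned infusion numbers would show total exposure only. The conclusion rests on the specific exemption overriding the general request to report all adverse events, and on some of these events not being judged serious. It does not depend on how anxiety is classified. This is a change worth considering, not one the trial depends on.

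**What to change.** In the Adverse Events section, limit the exemption to occurrences that did not stop the infusion for one of the listed intolerance reasons. State that occurrences which did stop it are reported as adverse events and count towards the multiple-minor-events trigger under Reporting procedure. This wording also settles severe anxiety without having to decide whether it is nervousness. Induced atrial fibrillation may stay exempt, since it is the study outcome and is already recorded in detail.

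The cost is one or two sentences and a few more adverse-event reports. No new data are needed, because the reason for stopping and the blood pressure readings are already collected at every infusion.

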- Appendix 4
 - o Letter to GP
